Patients with chronic pain in the US (100 million)⁷ have 2.6-times greater risk of suicide⁸⁻¹¹ and those on long-term opioid treatment are at even greater risk. Unfortunately, they often do not receive mental health treatment and thus do not receive suicide prevention interventions.¹² They do receive frequent healthcare for their pain^{13,14} providing an unmet opportunity to integrate suicide prevention into their treatment for pain. Problem-solving Treatment (PST) is an evidence-based approach that is available where patients want to receive treatment (e.g., primary care) and is efficacious for chronic pain.^{15,16} Importantly, PST targets problem-solving deficits which are known to increase risk of suicide, suggesting PST could be leveraged to reduce suicide risk. Deficits in problem-solving (an executive function used to find solutions to difficult issues)¹⁷⁻¹⁹ directly increase suicidal risk because they keep patients with active suicidal ideation from generating solutions to their problems (e.g., chronic pain), other than through suicide.^{3,20-22} Deficits in problem-solving also make it difficult to keep pain from impairing daily activities and social relationships. This indirectly increases suicide risk because impairment in daily activities increases feelings of burdensomeness and impairment in social relationships increases feelings of not belonging.²³ Feelings of burdensomeness and of not belonging are key theoretical pathways to suicidal behavior.²⁴

Research Design and Methods: This treatment study will be a randomized controlled trial with two arms: remote Problem-solving Treatment versus remote attentional control. Up to 1,000 Veterans will be screened and up to 60 Veterans will be enrolled. Subject participation will occur over the course of

approximately 9 months; Figure 1 outlines the study methods. Additionally, we will be asking enrolled Veterans to identify their support person (e.g., significant other, caregiver, spouse, partner, family member, friend) and we will invite the identified support person to complete a questionnaire and provide their perspective on the Veteran's problem-solving ability.

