For the support people that are interested in participating, we will mail them a confirmation letter detailing their appointment date/time, a study information sheet, the baseline assessment packet, and a copy of the written informed consent and HIPAA so they can review the study procedures and formulate questions prior to their subsequent telephone appointment. We are obtaining a waiver of documentation of consent for the Veteran's support person and will ask their support person, at the end

of reviewing the informed consent and answering any questions, if she/he agrees to participate. This will take approximately 10 minutes to complete and will primarily be conducted over the phone.

Inclusion Criteria: (a) has a VA primary care provider and has had an in-person visit with a VA provider in the past year; (b) pain that is: (b1) musculoskeletal, defined as regional (joints, limbs, back, neck) or more generalized (chronic widespread pain); (b2) moderately severe, defined as a Brief Pain Inventory (BPI) intensity item score of 5 or higher for either “average” or “worst” pain in the past week; and (b3) persistent, (i.e., ≥ 3 months); (c) active suicidal ideation defined as scoring a 2 to 4 on the C-SSRS.

Exclusion Criteria: (a) life-threatening condition; (b) severe cognitive impairment; (c) psychotic disorder; (d) pregnant or plans to become pregnant in the next year; (e) suicide attempt in the past year or hospitalization for suicide risk in the past year.

Randomization Procedures: Since randomization may fail to ensure equivalent levels of our primary dependent variable, we will enroll Veterans in matched pairs and use an urn randomization procedure designed to maximize the equivalence of groups based on selected matching criteria ⁵⁹ or “urns.” Matching will be based on screening suicidal ideation intensity and problem-solving ability with members of a pair falling within +/- 20% of one another to ensure that the distribution is comparable between groups. This matching rule permits wide latitude in scores, but if a Veteran is not matched s/he will be offered Problem-solving Treatment outside of the study. We will use the computer program developed for Project MATCH to generate the randomization schedule. The study coordinator will conduct the randomization. Research investigators (including the Principal Investigator) will be blind to study assignment.

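### Pairs and urn are combined without saying how, no concealment step is stated, and the between-arm effect size is not adjusted for the two balancing variables

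*Combined protocol and SAP*

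**What the plan says.** The Randomization Procedures section states: "we will enroll Veterans in matched pairs and use an urn randomization procedure". It adds: "Matching will be based on screening suicidal ideation intensity and problem-solving ability", with "members of a pair falling within +/- 20% of one another". On the mechanics it says: "We will use the computer program developed for Project MATCH to generate the randomization schedule", then "The study coordinator will conduct the randomization". Investigators are to be blind to assignment. For those without a partner: "if a Veteran is not matched s/he will be offered Problem-solving Treatment outside of the study".

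The section does not say:
- whether the two members of a pair must go to opposite arms;
- whether they are randomised together or one after the other;
- how the next assignment is concealed;
- what the 20% is a percentage of;
- when a Veteran counts as unmatched.

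Research Design and Methods sets the size ("up to 60 Veterans will be enrolled"), and Study Population gives 30 per group. The Data Analysis Plan compares arms by Cohen's d of the change, without significance tests. It names no pair term and no covariate. The only adjustment mentioned elsewhere is for other treatments, under Involvement in Alternate Treatments. Table 2 has the C-SSRS at screening and baseline, but the SPSI-R only from baseline onward.

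**The concern.** Pairing and urn allocation are different ways to obtain balance, and their weaknesses differ. Without a statement of how they combine, a reader cannot tell whether the second member's arm is predictable, or whether the split will be 30/30.

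The stakes are specific to this trial. Target engagement is judged on point estimates against fixed thresholds (d above 0.22 for self-report and support-person report, 0.15 for objective tests), with no test or interval to temper them. Selection through predictable allocation would pass straight into that decision. So would chance baseline imbalance that the estimate does not remove. A change score subtracts the outcome's own baseline, but that is not covariate adjustment, and for outcomes other than SPSI-R or C-SSRS intensity neither balancing variable enters at all.

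**Working it through.** **1. The plan's own figure.** 2 × 30 = 60 is consistent. The size rests on feasibility, and no match rate, balance or predictability figure is given, so there is nothing further to reproduce.

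**2. Predictability under the three possible readings.**
- *Opposite arms, in sequence.* The first member of each pair is a coin toss and the second is determined. Fixed in advance: 30/60 = 50%. Best-guess success: (30 × 0.5 + 30 × 1)/60 = 0.75.
- *Opposite arms, both at once.* Neither arm is fixed before the other, and 30 pairs give exactly 30/30. The first member's allocation waits for a partner.
- *Urn draw per Veteran.* The second member's arm is not determined, and both members may land in the same arm. In 2,000 simulated trials per setting (assumed urns UD(0,1), UD(1,1) and UD(1,3), with 1 or 4 strata), best-guess success is 0.55 to 0.60 and 0 to 4 of 60 assignments are certain. The split differs from 30/30 in 81% to 83% of trials, with a mean difference between arms of 3.5 to 3.8 Veterans.

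**3. The 20% rule.** The C-SSRS intensity range is given as 2 to 25. Relative to the score, a Veteran at 5 can match within 0.20 × 5 = 1 point. Relative to the range, the margin is 0.20 × 23 = 4.6 points. The text does not choose between them.

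**4. Matching.** The documents give no means or SDs. Assumptions: coefficients of variation 0.2 to 0.4, correlation between the two scores 0 or −0.3, first-come pairing, margin relative to the score. When 30 pairs are complete, 3.2 to 13.5 Veterans are unmatched, so 63 to 74 eligible Veterans are needed. The first member waits on average for 4.7 to 12.2 further Veterans. A separate run with the margin relative to the range left 2.7 of 60 unmatched, with a mean wait of 4.0.

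**5. Balance and precision.** In SD units with 30 per arm and baseline-to-post correlation r (assumed), simple randomisation gives in closed form:
- change score: SE = √[2(1 − r) × 2/30] = 0.258 at r = 0.5 and 0.200 at r = 0.7;
- baseline-adjusted: SE = √[(1 − r²) × 2/30] = 0.224 and 0.184.

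Simulation (3,000 runs, both coefficients of variation 0.3, same 60 Veterans):

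| Allocation | SD of standardised baseline difference | SE change, r = 0.5 | SE adjusted, r = 0.5 | SE change, r = 0.7 | SE adjusted, r = 0.7 |
|---|---|---|---|---|---|
| Complete, 30/30 | 0.24 | 0.253 | 0.225 | 0.199 | 0.189 |
| Urn, 4 strata | 0.18 | 0.248 | 0.231 | 0.192 | 0.187 |
| Pairs, opposite arms | 0.08 | 0.227 | 0.222 | 0.186 | 0.185 |

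Monte Carlo error of an SE is about 0.23/√(2 × 3,000) = 0.003, so the adjusted columns are nearly equal. The simulated adjustment used the baseline of the problem-solving outcome only.

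**6. Keeping the otherwise unmatched.** Randomising about 68 Veterans by urn gives an adjusted SE of 0.211 (r = 0.5), against 0.222 for 60 in pairs. That needs more than the stated maximum of 60.

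**7. Matching text against Table 2.** Of the two matching variables, only the C-SSRS has a screening entry. The SPSI-R is listed at baseline, 4 weeks, post-treatment and 6 months, and the four neuropsychological tests at baseline and post-treatment.

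**The case against.** The strongest reply is that this is missing detail rather than a flaw. Several stronger inferences are tempting, and the documents do not support them.

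- *Allocation concealment is lost.* The text never sends pair members to opposite arms, and it does not say that the coordinator enrols. Screening and consent fall to study team members generally. Half the assignments being foreseeable holds under one unstated reading, for someone who knows both the pairing and the first arm. What stands is that no concealment step is described; blinding the investigators does not supply one.
- *Pairing gains nothing.* It does gain: the SD of baseline imbalance is about 0.08, against 0.18 for the urn, and under the unadjusted change score pairs have the smallest standard error. What stands is that little of this advantage remains after adjustment.
- *Sixty enrolled cannot give 30 per group.* Thirty pairs with opposite arms do, and up to 1,000 may be screened to find them. It is the urn alone that does not assure it.
- *Veterans are left waiting for months.* No waiting period and no accrual rate are stated. Usual care continues, established providers are written to at consent, and unmatched Veterans are offered the treatment off study. Matching uses screening scores, so a partner could be found before baseline, and stale baseline data do not follow.

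The phone-screen packet is not part of the text available and may contain a problem-solving item. Even so, Table 2 and the matching rule disagree as written.

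**Conclusion.** The point holds as a gap in the allocation procedure, an avoidable weakness in the estimate, and an inconsistency over when problem-solving is measured. At worst, under the sequential opposite-arm reading, 30 of 60 assignments are foreseeable (75% best-guess success). Under independent urn draws the figure is 55% to 60%, but pairing then has little function and an equal split is unlikely.

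At r = 0.5, adjustment takes the standard error from about 0.248 to 0.231 with the urn and from 0.227 to 0.222 with pairs. The second difference is small against simulation error. At r = 0.7 both gains are smaller. These figures concern SPSI-R adjusted for its own baseline; other outcomes gain according to their correlation with the covariates. The unmatched counts (about 3 to 14) and waits (about 4 to 12 further Veterans) rest on assumed score distributions and are not document figures. Dropping the pairs is a trade-off, and the documents do not show it to be necessary.

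**What to change.** 1. **Adjust the estimate.** Estimate each between-arm effect size with baseline C-SSRS intensity and baseline SPSI-R as covariates. Table 2 already collects both, so the cost is one sentence and two degrees of freedom. State that baseline is completed before allocation. State the standardiser too, and do not use the residual SD: at r = 0.5 it is √0.75 = 0.866, so a difference of 0.22 would read as 0.22/0.866 = 0.25 against an unchanged threshold.
2. **If pairs are kept,** say that members take opposite arms and randomise both at the same moment, from a concealed schedule held by the collaborating statistician and not the coordinator. The cost is one request per pair, and the first member's allocation waits for the partner. The protocol should therefore say how long matching may take and what the 20% refers to.
3. **Reconcile** the matching rule with Table 2 on when, and with which instrument, problem-solving is measured.

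An acceptable option is to randomise each Veteran individually with the urn on the same two variables. This keeps otherwise unmatched Veterans and removes the wait. The price is looser balance and a split that may not be 30/30. With enrolment held at 60 the benefit lies in recruitment and representativeness; the lower standard error of 0.211 needs about 68 randomised.

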In addition, we will post general information about this study on other electronic media (e.g. the WRIISC website, Office of Public Health's (OPH) website, academic affiliations websites, and other VA and Veteran-related websites. We will reach out to Veteran Service Organizations (VSO) to develop a recruitment plan. We will also inform any Veteran who walks in or contacts the WRIISC interested to participate in research opportunities about this study. This includes Veterans who are participating in other research studies at the WRIISC.

Once potential participants are identified, we will mail a recruitment letter and may follow-up approximately 1 week later with a phone call inviting them to be screened for participation. For those who express interest, we will conduct an ~25-minute telephone screening to determine eligibility (see attached – Phone Screen Script and Phone Screening Questionnaire Packet). If a Veteran is ineligible at any point during the screening process, the member of the Study Team conducting the screening will stop and inform the Veteran of this. If eligibility is unclear at the end of the screening, a member of the Study Team will inform the Veteran that he/she will call him/her back. The member of the Study Team will then consult with the PI or another member of the Study Team, review the Veteran's medical chart (if needed) and call the Veteran to let him/her know whether he/she is eligible. If the Veteran is eligible at the end of the screening, the member of the Study Team will notify the Veteran of this and offer to schedule a day and time to complete the telephone-based informed consent process. When clinically appropriate we will also reach out to Veterans' established providers at screening to communicate the patient's active suicidal ideation. (If there is an increase in C-SSRS score from screening to baseline, we will notify the Veterans' established providers of this change).

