- **Baseline:** questionnaire packet, neuropsychological battery, and support person questionnaire packet will be collected at the start of the study (~2 hours for questionnaire packet and neuropsychological battery; ~5 minutes for the support person questionnaire packet)
- **4-week, mid treatment:** questionnaire packet will be collected after completion of the 4th session of either Problem-solving Treatment or attentional control (~30 minutes)
- **Post-treatment:** questionnaire packet, neuropsychological battery, and support person questionnaire packet will be collected after the 12th session of either Problem-solving Treatment or attentional control (~2 hours for questionnaire packet and neuropsychological battery; ~5 minutes for the support person questionnaire packet)
- **6-month follow-up assessment:** questionnaire packet will be collected ~6 months after the 12th session of either Problem-solving Treatment or attentional control (~1 hour)

See below for Table 2, which outlines when the measures and neuropsychological tests will be administered, along with a summary of each.

Table 2 – Measures administered at each timepoint

Domain	Study Instruments	Screening	Baseline	4 week	Post Treatment	6 Months
Aim 1: Primary Outcome	Social Problem-Solving Inventory Revised [SPSI-R] *		X	X	X	X
	Neuropsych Assessment: Emotional Go No-Go		X		X	
	Neuropsych Assessment: Means-End Problem-Solving Task [MEPS]		X		X	
	Neuropsych Assessment: Iowa Gambling Task		X		X	
	Neuropsych Assessment: Stroop Test		X		X	
Aim 1: Secondary Outcome	Interpersonal Needs Questionnaire [INQ]		X	X	X	X
Aim 2: Exploratory Outcome	Columbia-Suicide Severity Rating Scale [C-SSRS]	X	X		X	X
	Suicide Ideation Questionnaire [SIQ]		X	X	X	X
	Suicide-Related Coping Scale		X	X	X	X
	Pain Disability Index [PDI]		X	X	X	X
	Brief Pain Inventory [BPI]	X	X	X	X	X
Participation Characterization and Screening Instruments	Healthcare Access [HCA]		X		X	
	Demographic * / Treatment Survey	X	X		X	
	Post-Traumatic Stress Disorder Checklist [PCL]		X		X	
	The Patient Health Questionnaire-9 [PHQ-9]		X		X	X
	Patient Health Questionnaire [PHQ-15]		X		X	X
	World Health Organization Disability Assessment Schedule [WHO-DAS 2.0]		X		X	
	MOS Social Support		X		X	
	Audit-C		X		X	
	Cognitive Failures Questionnaire		X		X	X
	Coronavirus Stressor Survey	X				
Quality of Treatment Delivery	Working Alliance Inventory [WAI]			X	X	
	Patient Global Impression of Change [PGIC]				X	
	Client Satisfaction Survey				X	

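### Pairs are to be matched on problem-solving ability, but no problem-solving measure is scheduled before baseline, and the supplied text gives neither the matching score nor the order of baseline and randomisation

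*Combined protocol and SAP*

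**What the plan says.** Randomization Procedures gives the reason for matching: "Since randomization may fail to ensure equivalent levels of our primary dependent variable, we will enroll Veterans in matched pairs". The rule follows: "Matching will be based on screening suicidal ideation intensity and problem-solving ability", and the two members of a pair must lie within 20% of each other. Matching also decides who enters the trial, since "if a Veteran is not matched s/he will be offered Problem-solving Treatment outside of the study". The section does not say which instrument or score represents problem-solving ability.

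Under Subject Identification and Recruitment, "we will conduct an ~25-minute telephone screening to determine eligibility". The Assessments section introduces the schedule: "See below for Table 2, which outlines when the measures and neuropsychological tests will be administered". The Screening column of Table 2 is marked for four instruments only: the C-SSRS, the BPI, the Demographic/Treatment Survey and the Coronavirus Stressor Survey. The baseline assessment is placed at the start of the study, and the text does not state its order relative to pairing and randomisation.

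The Data Analysis Plan reports Cohen's d for change, within and between arms, without significance tests. It states no adjustment for baseline score. Target engagement is judged against d above .22 (self-report and support person) and d above .15 (at least two objective tests).

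**The concern.** A matching rule with a 20% tolerance needs one defined score for each Veteran at the moment pairs are formed. If the word screening covers both matching variables, the problem-solving score does not exist at that moment. If it covers ideation only, the study coordinator still has to choose among the SPSI-R total, its five subscales and four tests, and has to assume that baseline comes first.

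Two things are at stake. The first is balance on problem-solving, which is this trial's primary target and feeds a decision rule based on point estimates with small cut-offs. The second is the point at which an unmatched Veteran leaves: after a phone screen, or after consent and a full baseline. That affects the enrolment counts and who belongs to the intention-to-treat set.

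**Working it through.** **Randomisation text against the schedule (Table 2)**

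| Measure | Screening | Baseline |
|---|---|---|
| SPSI-R | blank | X |
| Emotional Go No-Go | blank | X |
| MEPS | blank | X |
| Iowa Gambling Task | blank | X |
| Stroop | blank | X |
| C-SSRS | X | X |

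Of the five Veteran-completed problem-solving measures, none is scheduled at screening and all five are scheduled at baseline. The ideation variable is available at screening, provided the screening C-SSRS includes the intensity items; Table 2 does not separate them. The length of the instrument agrees with the table: the SPSI-R has 52 items (Primary Outcomes) and would fit poorly in a call of about 25 minutes.

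**Raw baseline imbalance if problem-solving is left unbalanced**

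Inputs: 30 per group (Study Population); cut-offs of 0.22 and 0.15 (Data Analysis Plan). Simple 1:1 randomisation is assumed.

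- SE of the standardised baseline difference = sqrt(2/30) = 0.258.
- P(|difference| > 0.22) = 2 × (1 − Φ(0.22/0.258)) = 0.394, or 39%.
- P(|difference| > 0.15) = 2 × (1 − Φ(0.15/0.258)) = 0.561, or 56%.
- With 24 or 20 per arm analysed (assumed, since the documents give no attrition rate), the SE is 0.289 or 0.316. The two probabilities become 45% or 49% (above 0.22) and 60% or 64% (above 0.15).

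**Effect on the planned analysis of change**

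With equal variances and baseline-post correlation r, a baseline difference D shifts the expected between-arm difference in change by (1 − r) × D in size. The documents do not give r. I assume 0.5 to 0.87; the upper end is borrowed from the reliability quoted for the SPSI-R.

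- r = 0.5: 0.50 × 0.22 = 0.11 baseline SD, half of 0.22.
- r = 0.87: 0.13 × 0.22 = 0.029, about 0.03 baseline SD.

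**Gain from adjusting for baseline (30 per arm, baseline-SD units)**

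The SE of the change difference is 0.258 × sqrt(2(1 − r)). The SE adjusted for baseline is 0.258 × sqrt(1 − r²).

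| r | Change score | Adjusted |
|---|---|---|
| 0.5 | 0.258 | 0.224 |
| 0.87 | 0.132 | 0.127 |

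**The case against.** The strongest reply is that the word screening may attach to ideation intensity alone. That reading has a purpose: the C-SSRS is collected at both screening and baseline, so its time point must be named, whereas the SPSI-R has only one collection before treatment. Matching on baseline SPSI-R would then work if baseline comes before randomisation. This stands as a possible reading, but it still leaves the score and the sequence unstated.

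Second, the phone-screen packet and Figure 1 are not in the supplied text. Either could supply a measure or show the sequence. Table 2 also marks the Coronavirus Stressor Survey at screening only, while its footnote speaks of capturing it at baseline, so the protocol may use the two terms loosely. This also stands, and limits the claim to what the supplied text shows. If the packet does hold a problem-solving measure, Table 2 needs correcting.

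Third, the primary dependent variable in Randomization Procedures could mean C-SSRS intensity, since the Exploratory Outcome section uses that term for the later full trial. The point does not depend on this, because problem-solving is named as a matching variable either way.

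Fourth, a reader might infer from the 39% that chance imbalance alone is as likely as that to produce a false signal of target engagement. The plan does not support this. The 39% concerns raw baseline scores, and the decision rests on change. In change-SD units the shift is D × sqrt((1 − r)/2), so moving d by 0.22 needs D = 0.44 at r = 0.5 (probability about 9%) or D = 0.86 at r = 0.87 (below 0.1%). Most of the noise in the decision rule comes from having 30 per arm.

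**Conclusion.** The matching rule and the measurement schedule do not agree. On the natural reading, the problem-solving half of the matching cannot be run and the ideation half can. On the alternative reading, it can be run only after choices that the supplied text does not make. A reader might go further and conclude that the trial cannot be balanced at all. The documents do not support that: the problem-solving scores are collected at baseline, and the gap can be repaired.

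The consequence is moderate. A 0.22 SD imbalance left by the failed matching would move the change estimate by about 0.03 to 0.11 baseline SD, up to half the cut-off and not equal to it. This rests on an assumed correlation of 0.87 to 0.5, equal variances and, for the chance of such an imbalance, simple randomisation. It is still worth correcting, because the decision uses point estimates against cut-offs of 0.15 and 0.22 and no baseline adjustment is stated to absorb what matching misses.

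**What to change.** 1. In Randomization Procedures, name the score and the time point. Either state that problem-solving matching or urn balancing uses the baseline SPSI-R total, and that pairing and randomisation follow completion of the baseline packet, with ideation left on the screening C-SSRS if preferred. Or add a named problem-solving score to the Screening column of Table 2.
2. In the Data Analysis Plan, replace the unadjusted between-arm change-score d with an estimate for each target adjusted for its own baseline score and the matching scores. State which SD divides the adjusted difference, because the cut-offs are in SD units.

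Cost: the first option needs no new data, but it delays randomisation until the packet is complete. Veterans who cannot be matched will by then have consented and completed about 2 hours of assessment, paid at $50, before leaving the study, so their number should be tracked and reported. The second option avoids this but lengthens the phone screen. The adjustment uses scores already collected and costs only a few degrees of freedom.
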